## **V.II. Devices to be used**

Two fluoroscopes (BV Pulsera, Philips, Eindhoven, Netherlands) will be used to capture images of the wrist at each extreme motion. The fluoroscope has been developed to produce real-time 1K x 1K imaging resolution and has an image intensifier diameter of 31 cm. When using the two fluoroscopes to obtain orthogonal images, the total imaging volume can reach up to 30cm x 30cm x 30cm. Such a system will allow the investigator to capture the two images simultaneously, thus minimizing the amount of time that the subject must remain still. The operator will perform the imaging via a switch. The distance between the source of radiation and the personnel will be approximately 2 meters. The investigator will also be protected from radiation exposure with appropriate lead shielding. In order to monitor radiation exposure, badges will be worn during the imaging process.

The fluoroscope has a clearance of approximately 1 meter between the X-ray source and the receiver, allowing the subject to be imaged by the fluoroscopes simultaneously throughout the entire range of motion.

After scanning, the collected imaging data from the CT imaging and the fluoroscopy will be transferred to the computers of the Bioengineering Laboratory for further data processing. Each subject will be assigned a code for data storage and further processing, ensuring confidentiality. The laboratory computers are only accessible to the Bioengineering Laboratory members. The imaging files from this study will furthermore

be specifically password protected and therefore will only be accessible to the investigators.

The images of the wrist at each performed motion will be entered into the Rhinoceros® software program (Robert McNeel & Associates, Seattle, WA), where the contours of the wrist bones will be outlined and digitized. The digitized data will then be used to construct the contour lines of the bony cross-sections using piecewise polynomial curves. Reconstruction of the bony surfaces will be achieved by transforming these curves into piecewise polynomial surfaces using the Rhinoceros® program.

## **V. Biostatistical Analysis**

A total number of 10 subjects will be considered for this pilot study. Post-hoc we will determine if our sample size is sufficient in order to perform a multivariable logistic regression analysis using the rule of thumb to avoid fitting a model with too many degrees of freedom in the modeling process. In case we need to enroll higher number of subjects, we will inform the IRB to obtain approval prior to proceeding.

Data obtained for statistical analysis will include scanning of each wrist at different positions beside a grip and leaning position. At each respective position, translations, rotations, and gap formation will be measured.

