#### I. Background and Significance

The kinematics of scapholunate interosseous ligament (SLIL) injuries are poorly understood. Some patients are relatively asymptomatic while other patients have pain and difficulty with pushing and loading of the wrist. Even more confounding, some patients with complete injury and dissociation of the scaphoid from the lunate may be symptom free, while some patients with partial injuries describe substantial wrist dysfunction.

The kinematics of the wrist may provide insight into this dysfunction. *In vivo* kinematics of the normal wrist has been studied previously, but few studies have characterized the wrist with a SLIL injury. In addition, there are few studies evaluating validated patient-rated outcomes for patients with SLIL injury. The goal of this study would be to evaluate to what degree kinematic abnormalities affect patient-rated outcomes.

A dual fluoroscopic imaging technique has been used to study the kinematics of various joints and quantify the variations associated with ligament insufficiency or ligament reconstruction. We propose an *in-vivo* study on the wrist of patients with SLIL injury. This technique should identify any changes in carpal kinematics and may be able to be correlated to signs and symptoms of pain and osteoarthritis.

Our technique provides a direct technique for measurement of wrist kinematics. The system is not only a viable solution for the investigation of fully dynamic joint kinematics, but also has a low radiation dosage, is non-invasive, and can be constructed using any pair of readily available fluoroscopes. Thus, the DFIS provides an easy and powerful tool for accurately determining 6DOF positions of healthy, injured, and surgically treated wrists in 3D space.

- (1) Wolfe SW et al. *In vivo* scaphoid, lunate, and capitate kinematics in flexion and extension. *J Hand Surg Am* 2000; 25A : 860-9.
- (2) Crisco JJ et al. *In vivo* radiocarpal kinematics and the dart-thrower's motion. *J Bone Joint Surg* 2005; 87A: 2729- 2739.
- (3) Moritomo H et al. Capitate-based kinematics of the midcarpal joint during wrist radioulnar deviation: An *in vivo* three-dimensional motion analysis. *J Hand Surg* 2004; 29A: 668-675.
- (4) Li G et al. *In vivo* articular cartilage contact kinematics of the knee: an investigation using dual-orthogonal fluoroscopy and magnetic resonance image-based computer models. *Am J Sports Med.* 2005 Jan;33(1):102-7.

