## II. Specific aims

This represents a study on subjects with scapholunate interosseous ligament (SLIL) injury and *in-vivo* joint kinematics analysis based on a new three-dimensional imaging method which will integrate images from CT scan and from dual-orthogonal fluoroscopy.

We hypothesize that there is no relationship between *in vivo* kinematic abnormalities and patient-rated outcomes for scapholunate interosseous ligament injuries (SLIL)

Our secondary null hypotheses are that: There are no kinematic differences between subjects with unilateral, symptomatic, full thickness scapholunate ligament tears in comparison to the contralateral wrist without scapholunate ligament injury.

We also aim to answer to the below questions:

- What are baseline validated outcomes for subjects with SLIL injury?
- What are baseline physical measures (range of motion, Jamar Dynamometry)?

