## III. Subject selection

In this pilot study, we will recruit 10 subjects with the below inclusion criteria:

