## IV. Subject Enrollment

A total number of 10 subjects will be considered for this pilot study. Post-hoc we will determine if our sample size is sufficient in order to perform a multivariable logistic regression analysis using the rule of thumb to avoid fitting a model with too many degrees of freedom in the modeling process. In case we need to enroll higher number of subjects, we will inform the IRB to get the approval beforehand.

Participation is voluntary. Prospective subjects will be invited in the clinic after being diagnosed and will be provided with a flyer explaining the study. The treating physician will ask the subject's permission to have researchers contact them. A researcher who is IRB approved study staff will contact the subject to confirm eligibility, explain the study, and set up the first study appointment.

At the first study visit, the study will first be explained in detail. After reading the consent form, subjects will be able to ask additional questions. [REDACTED] who is an expert research scientist with more than 9 years of experience in Bioengineering Lab and is an IRB approved study staff will obtain informed consent.

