### **V.I. Study visits**

Subjects with a unilateral, full thickness scapholunate ligament tear documented by radiographs of the interest and contralateral wrist, MR arthrogram, or MRI of the interest wrist as well with no history or radiographic evidence of wrist injury will be enrolled. A CT scan of both wrists will be obtained. The contralateral wrist will serve as a matched control.

[figure not shown]
Participation in this study will require two visits at the Massachusetts General Hospital. A research assistant who is IRB approved study staff will contact the subject by telephone and/or email to schedule the visits and will ask the subject whether he/she would prefer to do the CT scan and Fluoroscopy in either one longer session or two separate shorter sessions.

The *first visit* after enrolling in this study will be to undergo a CT scan of both wrists. This visit will last approximately 60 minutes. The subject will lie motionless with outstretched hands on a table that slides into a square donut frame for about 2 minutes. Subjects will complete the PRWE, DASH, and SF-12 questionnaires. Questionnaires will be completed on paper. Range of motion of both wrists will be assessed using a goniometer. Grip force of both wrists will be assessed using Jamar Dynamometer. Pinch force will be assessed for both sides using pinch gauge.

The *second visit* will last approximately 60 minutes. Images of the both wrists will be taken with fluoroscopes, which are able to take digital x-ray pictures. During this visit, the subject will perform fully dynamic activities as described below, while the fluoroscopes take digital x-rays, one wrist at a time:

[REDACTED]

[REDACTED]

Each subject will be given a radiation protection apron, a protective thyroid shield, and protection for genital region. The first and second visits can be done in the same day or 2 separate days, whichever is more convenient for the subject.

The data obtained from these visits will be transferred to a computer and will be used to reconstruct three-dimensional wrist models. It will help researchers better understand the association of small bones in the wrist and whether any changes happen in their related movements after SLIL injury.

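### The only analysis named is a multivariable logistic regression behind a post-hoc size check; for a binary patient-level outcome 10 subjects would fail that check under usual rules, and no fallback is given

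*Combined protocol and SAP*

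**What the plan says.** Section I frames the question as one of degree: "The goal of this study would be to evaluate to what degree kinematic abnormalities affect patient-rated outcomes". Section II turns this into a first hypothesis that begins "We hypothesize that there is no relationship between" and goes on to kinematic abnormalities and patient-rated outcomes. A secondary null hypothesis follows: "There are no kinematic differences between subjects with unilateral, symptomatic, full thickness scapholunate ligament tears in comparison to the contralateral wrist". Two descriptive aims, on baseline questionnaire results and physical measures, complete the section.

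The size is fixed in section III: "In this pilot study, we will recruit 10 subjects". The outcome instruments are in section V.I: "Subjects will complete the PRWE, DASH, and SF-12 questionnaires". The same section sets up the comparison between wrists: "The contralateral wrist will serve as a matched control".

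The only statistical method is in V. Biostatistical Analysis, and section IV states it in nearly the same terms: "Post-hoc we will determine if our sample size is sufficient in order to perform a multivariable logistic regression analysis using the rule of thumb". The stated purpose of the check is to avoid a model with too many degrees of freedom. Section IV adds "In case we need to enroll higher number of subjects, we will inform the IRB to get the approval beforehand", and the statistical section has an equivalent sentence. The statistical section then describes the kinematic data to be measured at each position.

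No rule value, outcome variable, cut-off, predictor list, fallback, correlation or paired test is stated anywhere. The statistical section carries no redaction mark. The blacked-out block in V.I follows the sentence that introduces the wrist activities, so it is unlikely to hide an analysis.

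**The concern.** A rule-of-thumb check on a logistic model normally counts events per predictor, and with 10 subjects that count has a ceiling that can be worked out before anyone is enrolled. Deferring the check until after data collection therefore adds no information for a binary patient-level outcome. It only delays the finding that the one named method cannot be used for the first hypothesis.

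The model also fits the questions poorly. The first asks how strongly two quantities are related, the questionnaires yield scores, and no dichotomy is defined. The second compares two wrists of the same person, and no paired form of analysis is named.

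What is at stake is interpretability. If the check fails, the first hypothesis is either reported only descriptively, analysed by a method chosen after the data are seen, or deferred to a larger sample of unstated size. With three questionnaires, three families of kinematic measures and several positions, the second route leaves a great deal of choice. The study is a non-interventional pilot, so no treatment decision depends on this, and the descriptive aims are untouched.

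**Working it through.** **Inputs from the documents.** 10 subjects (sections III, IV and V. Biostatistical Analysis); two wrists each, the contralateral one a matched control (V.I).

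**Assumptions, because the documents give no figure.** Events per variable (EPV) of 5, 10 or 20; a binary outcome per patient; at least two predictors in a multivariable model.

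**The plan's own figure.** The size of 10 is stated without alpha, power, effect size or rule value, so no formula can reproduce it.

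**Binary outcome per patient.** Terms supported = smaller class / EPV. The smaller class is at most 5.
- Two predictors: 5/2 = 2.5 events each.
- Split 5 to 5: 5/5 = 1.0, 5/10 = 0.5, 5/20 = 0.25 terms.
- Split 3 to 7: 3/5 = 0.6, 3/10 = 0.3, 3/20 = 0.15 terms.

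No value in the range allows two predictors.

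**Other readings.**

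| Reading | Effective size | Terms at 5 / 10 / 20 |
|---|---|---|
| Rule counting subjects | 10 | 2 / 1 / 0.5 |
| Ordinal logistic, 10 distinct scores | 10 - 10/10² = 9.9 | 1.98 / 0.99 / 0.50 |
| Matched-pair (conditional) logistic, 10 pairs | 10 | 2 / 1 / 0.5 |
| Ordinary wrist-level logistic, 10 versus 10 | 10 | 2 / 1 / 0.5 |

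Only the most lenient value reaches two terms, or about two. Both wrist-level readings make injury status the outcome, so they address the secondary hypothesis and not patient-rated outcomes; the ordinary one also ignores the pairing.

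**Subjects needed for two predictors of a binary outcome.** N = 2 × EPV / smaller-class proportion.
- Even split: 2 × 5/0.5 = 20, 2 × 10/0.5 = 40, 2 × 20/0.5 = 80.
- Smaller class 30% (assumed): 10/0.3, 20/0.3 and 40/0.3, rounded up to 34, 67 and 134.

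**Precision of a simpler analysis with 10 subjects.**
- Pearson correlation of 0, Fisher z: tanh(1.96/√7) = 0.63, so the 95% CI is -0.63 to 0.63.
- Observed correlation of 0.5: tanh(0.549 ± 0.741) gives -0.19 to 0.86.
- Paired difference: half-width 2.262/√10 = 0.72 SD of the differences.

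**Power with 10 subjects, two-sided 5%.**
- Pearson (simulation, bivariate normal): about 33% at r = 0.5 and 68% at r = 0.7.
- Paired t (noncentral t): about 29%, 62% and 80% at mean differences of 0.5, 0.8 and 1.0 SD of the differences.

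**The case against.** The best defence is that the plan does not commit to the regression. It makes the model depend on a check meant to prevent overfitting, calls the study a pilot, and requires IRB approval before enrolling more. If the check fails, a descriptive report is consistent with the text. This stands in part, and it rules out several stronger readings:

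- A reader might infer that an overfitted model will be run. The documents do not support that, because the check exists to stop it.
- A reader might infer that the only outcomes are analysis by hindsight or open-ended enrolment. A descriptive report is a third outcome, and enlargement is not unchecked.
- A reader might infer that no logistic model could pass. A per-subject rule or a matched-pair model nominally reaches two terms at 5 per term. The matched-pair model, however, does not address patient-rated outcomes.
- A reader might infer that a non-significant result will be reported as proof of no relationship. No passage says so. The section goes on to secondary null hypotheses, so the first statement reads naturally as a conventional null. Misreading is a risk, not a stated rule.
- The absence of a questionnaire score from the data description in the statistical section is weak evidence of omission. That sentence is not exhaustive, and V.I names the instruments.

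What the defence does not supply is an analysis. The pilot label excuses a small sample, but the protocol chose to state two hypotheses. The enlargement clause carries no trigger, target or rule value.

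**Conclusion.** The point holds and should be fixed, at moderate rather than critical severity. For a binary patient-level outcome, 10 subjects give at most 2.5 events per predictor in a two-predictor model, below every assumed rule from 5 to 20. Meeting such a rule would take at least 20 subjects, and 40 or 80 at 10 or 20 events per variable, even with an even split. When the check fails, the first hypothesis has no prespecified analysis. The secondary hypothesis has no stated form of analysis that respects the pairing.

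The conclusion that the check fails rests on the binary outcome and on the assumed rule values, neither of which the plan defines. The absence of an outcome, predictors and a fallback does not rest on any assumption.

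**What to change.** In section IV and in V. Biostatistical Analysis, replace the logistic regression and its post-hoc check with the following.

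1. **First hypothesis.** Name in advance one questionnaire score, kept numeric (for example PRWE), and one kinematic measure at one position (for example the injured-minus-contralateral difference in scapholunate gap). Report their Spearman correlation with a 95% CI, state how the interval is computed, and present the result as pilot estimation. State that a non-significant result will not be reported as evidence of no relationship.
2. **Secondary hypothesis.** Report the mean injured-minus-contralateral difference in one measure named in advance, with a paired-t 95% CI. Use the Wilcoxon signed-rank test as a sensitivity analysis.
3. **Everything else.** Label all other scores, measures and positions exploratory.

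If the option to enrol more is kept, a target size should go with it. The precision of the correlation offers a basis: the half-width around a Pearson r of 0 is 0.63 with 10 subjects, tanh(1.96/√17) = 0.44 with 20 and tanh(1.96/√27) = 0.36 with 30.

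The cost is protocol wording; no further data are needed. Multivariable adjustment is given up, although for a binary patient-level outcome 10 subjects could not have supported it under these rules. The change does not make the first hypothesis answerable at this size, because power remains low. The gain is an interpretable, prespecified estimate, not a definitive test.

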## **VI. Risks and Discomforts**

Radiation risks: The following is the revised statement from █ of the Radiation Safety Committee: The subject will be exposed to radiation from the x-rays during fluoroscopy. A milliSieverts (mSv) is a unit of measure of radiation dose. The worldwide average natural background dose from the earth and the sky for a human being is about 3 mSv per year.

For subjects, the total amount of radiation exposure from full participation in this study is equal to a whole body exposure of 0.071 mSv from fluoroscopy. This amount of radiation is about the same one would normally receive in 9 days from natural background sources from the earth and the sky.

The fluoroscopy scanning will be performed in a room specifically dedicated to this equipment and the study. No other laboratory work will be performed in this room during testing. The only persons present during scanning will be the subject and the personnel operating the fluoroscope. The room is located at the end of a hallway and its door will be closed while operating the fluoroscope.

The subjects will be provided with lead aprons (0.5 mm thickness), lead thyroid shields and lead gonad shields for protection against radiation exposure.

After positioning the subjects, the personnel handling the fluoroscope will be performing the scan via a hand switch. The distance between the source of radiation and the personnel will be approximately 2 meters. Furthermore, the personnel will be protected with lead aprons (0.5 mm thickness) and lead thyroid shields. In order to monitor exposure of personnel, radiation exposure badges will be worn during the scanning process.

The radiation protection aprons, thyroid shields and gonad shields have been specifically purchased for this study and will only be used for the purposes of this study.

[name] or [REDACTED] or one on the research fellows which is approved by IRB as a study staff will have carefully screened prospective subjects for possible contraindications at the initial evaluation. These contraindications include pregnancy and breast feeding women. Subjects with these contraindications will be excluded from the study.

Adverse events will be reported promptly to the IRB according to Partners Human Research Committee guidelines.

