### Exclusion Criteria

- Patients < 18 years old
- Patients with partial thickness scapholunate ligament tears
- Patients with radiographic arthrosis
- Patients with prior wrist surgery
- Pregnancy

Subjects will be identified from the clinical practice of [name], [REDACTED], [REDACTED], [REDACTED], and [REDACTED]. Plain radiographs of the interest wrist and contralateral wrist and MRI of the interest wrist will be performed to confirm the diagnosis as a routine practice. Consent procedures are detailed below.

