The CT scan of the contralateral side is designed to answer research questions. This CT scan is not a substitute for one a doctor would order. However, if we believe that we have found a medical problem in the CT, we will ask a doctor who is trained in the reading of CTs, a radiologist, to help us review the images. If the radiologist thinks that there may be abnormalities in the CT images, we will contact the subject and will help him/her get medical follow-up for the problem.

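### The total radiation dose in Section VI covers fluoroscopy only and leaves out the study CT of both wrists, so it is too low

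*Combined protocol and SAP*

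**What the plan says.** Section VI opens its radiation statement by naming one source: "The subject will be exposed to radiation from the x-rays during fluoroscopy". It then says that "the total amount of radiation exposure from full participation in this study is equal to a whole body exposure of 0.071 mSv from fluoroscopy". For scale it adds that "The worldwide average natural background dose from the earth and the sky for a human being is about 3 mSv per year", and concludes: "This amount of radiation is about the same one would normally receive in 9 days from natural background sources from the earth and the sky". CT is not mentioned anywhere in Section VI.

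Section V.I (Study visits) describes a second source of ionising radiation. Among the study procedures it lists "A CT scan of both wrists will be obtained", and the purpose of the first visit "after enrolling in this study will be to undergo a CT scan of both wrists". On the uninjured side it is explicit: "The CT scan of the contralateral side is designed to answer research questions".

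Section III (under Exclusion Criteria) describes the routine imaging that confirms the diagnosis: plain radiographs of both wrists and MRI of the affected wrist. CT is not on that list.

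**The concern.** A dose described as the total for full participation should add up every ionising procedure that a subject undergoes because of the study. Sections V.I and VI disagree on what those procedures are. Section V.I has two, CT and fluoroscopy, while the Section VI figure covers one.

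This figure is the only quantified risk in the protocol, and Section VII expects no direct benefit to subjects. The judgement that participation is acceptable therefore rests on the risk side. A reader of Section VI would conclude that fluoroscopy is the only exposure and that 9 days of background is the whole burden. No hypothesis, sample size or analysis is affected.

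**Working it through.** **Inputs from the documents**
- Stated total dose: 0.071 mSv, attributed to fluoroscopy (Section VI).
- Natural background: about 3 mSv per year (Section VI).
- Stated equivalent: 9 days (Section VI).
- CT of both wrists at the first study visit (Section V.I).
- CT dose: not given anywhere.

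**Step 1. Reproduce the plan's figure.** Equivalent days = dose / annual background x 365.

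0.071 / 3 x 365 = 8.64 days, which rounds to the stated 9. The conversion is correct, and it uses the fluoroscopy dose with nothing added.

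**Step 2. Is the CT part of the study or part of routine care?** It takes place after enrolment, as a study visit. Section III leaves it out of routine imaging, and Section V.I assigns the contralateral scan to research. Even if the affected-side scan were counted as clinical care, which the text does not say, the contralateral scan would still belong in the total.

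**Step 3. Direction.** Corrected total = 0.071 + D, where D is the CT dose and D > 0. The total must rise.

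**Step 4. How much CT dose would change the stated 9 days?** The equivalent stops rounding to 9 at 9.5 days, which is 9.5 x 3 / 365 = 0.0781 mSv. That leaves 0.0781 - 0.071 = about 0.007 mSv for CT.

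**Step 5. Illustrative size.** Let c be the dose per wrist CT, an assumption ranging from 0.01 to 0.10 mSv. The two scans are treated as additive, so D = 2c for both wrists and D = c for the contralateral wrist alone.

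| Assumed c (mSv) | Both wrists: total = 0.071 + 2c | Days | Ratio to 0.071 | Contralateral only: total = 0.071 + c | Days | Ratio to 0.071 |
|---|---|---|---|---|---|---|
| 0.01 | 0.091 | 11.1 | 1.3 | 0.081 | 9.9 | 1.1 |
| 0.05 | 0.171 | 20.8 | 2.4 | 0.121 | 14.7 | 1.7 |
| 0.10 | 0.271 | 33.0 | 3.8 | 0.171 | 20.8 | 2.4 |

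For a wider assumption, a combined CT dose of 0.5 mSv would give 0.571 mSv, which is 69.5 days and 8.0 times the stated total. The ratios depend entirely on the assumed dose. They are large because the stated figure is itself small.

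**The case against.** The strongest reply is that nothing has been miscalculated. The figure carries its source, fluoroscopy, in the same sentence, and nothing suggests that 0.071 mSv is wrong for that procedure. This is right as far as it goes: the error is one of scope. But the sentence is about the total for full participation, and naming the source does not tell the reader that a second exposure exists.

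The second reply is that the size is assumed throughout. This stands. The documents support only a total above 0.071 mSv by an unknown amount. The per-wrist model is also a simplification. Section V.I reads as though both hands may be scanned in one acquisition of about 2 minutes, in which case the contralateral share need not be half.

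Third, the consent pages are not in the review copy, and neither is the submission behind the Radiation Safety Committee statement. CT may have been disclosed there. That limits what can be said about what subjects and the IRB were told, but it would not make the total in Section VI correct. If the consent form does give a CT dose, the two documents disagree.

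Finally, the consequence may be slight. Even 0.271 mSv is about 9% of a year's background (0.271 / 3), and the pregnancy questioning and urine testing under Study procedures apply at each visit, including the CT visit. Both points are fair. They bear on how serious the hazard is and leave the stated total still wrong.

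**Conclusion.** The concern holds. Section VI presents as a total a dose that covers one of the two ionising study procedures in Section V.I, so both the mSv figure and the 9-day equivalent are too low. The direction is certain, because it requires only that the CT dose is above zero. The omission includes at least one exposure that exists purely for research, the contralateral CT.

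The size is unknown from the documents and may be small in absolute terms. The illustrative 0.091 to 0.271 mSv (11 to 33 days) rests on an assumed 0.01 to 0.10 mSv per wrist and on additive scans, and it should not be read as an estimate. The correction is needed because a quantified safety statement is wrong as written, whatever the CT dose proves to be.

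**What to change.** Ask the Radiation Safety Committee for the effective dose of the bilateral wrist CT as it will be performed, and have the statement reissued. Section VI should then name both CT and fluoroscopy as sources, give each component and their sum, and recompute the background equivalent from that sum. Carry the revised figures into the consent form, or check that they agree with what is already there. If the affected-side CT is considered clinical care, Section V.I should say so, and the total should still include the contralateral scan.

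Until the CT dose is available, describe 0.071 mSv as the fluoroscopy component, drop the claim that it is the total, and state that CT adds to it.

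The cost is one dose calculation and a wording amendment. The stated risk becomes somewhat less favourable. Nothing in the design, the measurements or the analysis has to change.
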